Trial Design	Randomised, controlled, vaccine co-administration study with blinding
Trial Participants	Adults aged 50 and above with or without stable co-morbidities
Sample Size	
A total of 960 participants, consisting of two serology sub-cohorts (COVID-19, n=360; influenza, n=720); cell-mediated immunity (CMI) cohort CD4+ T cells (n=150) and exploratory immunology cohort (n=150). Participants will be randomised in a 1:1:2:2:2 ratio to one of five groups; 120 participants to groups 1 and 2, and 240 participants to groups 3-5. Only 120 participants in group 3 will progress to the second and third vaccination time points required to assess C19/RZV co-administration.
 
 • All five groups will receive two doses of RZV (except participants in group 3 who do not progress after the first vaccination timepoint and will not have any RZV doses as part of the trial) • At the first and second vaccination timepoints, participants will receive two injections (combinations of RZV, C19, aQIV or placebo)

	
 At the final vaccination visit participants will receive one injection (either second RZV, if in the vaccination season aQIV or C19 or placebo)
Planned trial period	
5 months per participant (following from the first study vaccination)
 
6 months for recruitment (following from first participant recruited)
 
28 months including trial set up and close down

	Objectives	Outcome Measures	Timepoint(s)
Co-primary immunogenicity outcomes	Immunogenicity, measured by S-binding total Ig, 1 month-after C19 vaccine given alone compared to co-administration with RZV (first or second dose)	Anti-spike total Ig	Days 0, 28, 56 & 84 Groups 1-3
	Immunogenicity, measured by haemagglutination inhibition assay (HAI), 1 month after aQIV for 3 of the strains included in the vaccine; HAI influenza A H3N2, HAI influenza A H1N1 and HAI influenza B	HAI	Days 0, 28, 56 & 84 Groups 3-5

	Victoria given alone compared to co- administration with RZV		
	Immunogenicity of 2 doses RZV vaccine, 1 month after the second dose, given alone, compared to co-administration with C19 or aQIV with either first or second dose of RZV	Anti-gE Ig	Days 0, 56, 84, & 140 Groups 1-5

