5. Solicited local adverse reactions over 7 days after 1st and 2nd doses of RZV given alone compared to co-administration with either C19 vaccine or aQIV.
6. Solicited systemic AEs over 7 days after 1st doses of RZV given alone compared to co-administration with either C19 vaccine or aQIV.
7. Solicited systemic AEs over 7 days after 2nd doses of RZV given alone compared to co-administration with either C19 vaccine or aQIV.
8. Grade 3 and 4 SSR after 1st RZV dose in group 1 (day 56), 2 and 5 (day 0) compared to grade 3 and 4 SSR after 1st dose of RZV with C19 vaccine in group 3 (day 56)
9. Grade 3 and 4 SSR after 2nd dose of RZV in group 1, 3 (day 112) and 4 (day 56) compared to grade 3 and 4 SSR after 2nd dose RZV with C19 vaccine in group 2 (day 56).
10. Grade 3 and 4 SSR after 1st dose RZV in group 1 (day 56), 2 and 5 (day 0) compared to grade 3 and 4 SSR after 1st dose of RZV with aQIV in group 4 (day 0).
11. Grade 3 and 4 SSR after 2nd dose of RZV in group 1, 3 (day 112) and 4 (day 56) compared to grade 3 and 4 SSR after 2nd dose RZV with aQIV in group 5.
12. Days off work (for participants in employment) due to vaccine related AEs associated with different schedules under study over a period of 140 days .
13. Quality of life score over the 7 days after 1st and 2nd doses of RZV given alone compared to co-administration with either BNT162b vaccine or aQIV.
14. Unsolicited AEs up to 30 days after 1st and 2nd doses of RZV given alone compared to co-administration with either C19 vaccine or aQIV.
15. Serious adverse events and AEs of special interest including potential immune mediated disorders (pIMD) from after first vaccination until the study end.

16. Describe participant and study nurse attitudes to vaccine co-administration.

4. Primary and secondary outcomes

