4.1 Primary outcome

Part A: Assessment of co-administration of COVID-19 and RZV

Co-Primary Endpoints

1) Immunogenicity of C19

Anti-S protein Ig concentrations expressed as Geometric Mean Concentrations (GMCs) for both strains in C19 vaccine/RZV (first or second dose, groups 2 & 3) and C19 vaccine alone (group 1), will be used to calculate between group ratios expressed a geometric mean ratio (GMR), at 1 month after vaccination with C19 vaccine.

2) Immunogenicity of RZV

Anti-gE Ig concentrations expressed as GMCs after co-administration of C19 vaccine/RZV (first or second dose) and RZV alone, 1 month after 2nd dose of RZV, and between-group ratios expressed as GMRs.

Success criteria:

Part A of the trial will be classified as a success if both of the following meet the success criteria:

- 1) The combined administration of C19 vaccine and RZV (first or second dose) will be considered non-inferior to C19 vaccine alone if the lower limit of the 95% confidence interval for the (GMR) of anti-S protein Ig concentrations exceeds 0.67, the standard WHO non-inferiority margin for recommendation of new vaccines.⁷, AND

2) The combined administration of C19 vaccine and RZV (first or second dose) will be considered non-inferior to RZV alone if the lower limit of the 95% confidence interval for the GMR of Anti-gE Ig concentrations exceeds 0.67.

3) Safety of RZV

The rate of grade 3 and 4 solicited systemic adverse reactions (Table 2) after C19 vaccine/RZV (first or second dose, groups 2 and 3) and RZV alone 7 days after vaccination (groups 1-5) This is a descriptive outcome.

Table 2 Solicited AEs collected on post vaccination diary cards

Systemic solicited AEs
Fatigue
Fever
GI symptoms†
Headache
Myalgia
Shivering

†Gastrointestinal symptoms include nausea, vomiting, diarrhoea and/or abdominal pain

Note: The above AEs are assumed to be related and will be classed as adverse reactions.

Part B: Assessment of co-administration of adjuvanted influenza vaccine and RZV

Co-Primary Endpoints

1) Immunogenicity of aQIV

HAI titres expressed as GMCs in aQIV/RZV (first or second dose, groups 4 & 5) and aQIV alone (group 3) will be used to calculate between group ratios, expressed as GMR at one month after aQIV vaccination.

2) Immunogenicity of RZV

Anti-gE Ig concentrations expressed as GMCs after co-administration of aQIV/RZV (first or second dose) and RZV alone, 1 month after 2nd dose of RZV, and between-group ratios expressed as GMRs.

Success criteria:

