4.2 Secondary outcomes

Immunological

- Vaccine response rate (VRR) to RZV as measured by anti-gE, 1 month after vaccination with 2nd dose of RZV, in all groups and between-group differences. VRR defined as a 4-fold increase in post-vaccination anti-gE compared to pre-vaccination anti-gE

concentration for participants who are seronegative at baseline then a 4-fold increase compared to a cut-off value for seropositivity.

- Exploratory evaluation of cell-mediated immunology, CD4+T-cells responses 1 month after the 2nd dose of RZV as measured by intracellular cytokine staining (ICS) compared to RZV given alone or concomitantly for either first or second dose
- S and N-protein immunoglobulin, before and 1 month after vaccination with a single dose of RZV and aQIV to assess for exploratory immunology T-cells against SARS-CoV-2 provided by RZV vaccine or aQIV

Safety

- Percentage of participants reporting grade 3 and 4 SSR after first dose of RZV alone compared to first dose co-administered with either C19 vaccine or aQIV.
- Percentage of participants reporting grade 3 and 4 SSR after second dose of RZV alone compared to second dose co-administered with either C19 vaccine
- Percentage of participants reporting solicited local and systemic Aes, 7 days after each vaccination time point by group and between-group ratios
- Unsolicited Aes for 30 days after vaccination
- Serious adverse events throughout the study period
- Adverse events of special interest (pIMDs) throughout the study period
- Days off work (for participants in employment) during the study period reported as related to vaccination
- Quality of life score following vaccine co-administration compared to single vaccination in the 7 days after vaccination

Qualitative

Outcomes will include but not be limited to

- Participant acceptance of multiple vaccinations (2 or more) for future routine vaccinations
- Trial staff perceptions on offering multiple vaccinations (2 or more) for future routine vaccinations

5. Plan of Investigation

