13.4 Plan of analysis – primary and secondary outcomes

Analyses will be performed on an intention-to-treat basis and will be directed by a pre-specified statistical analysis plan (SAP). Results will be reported in accordance with CONSORT reporting guidelines.^{10, 11}

Co-primary and secondary immunogenicity outcomes will be analysed using a mixed regression model, with treatment group, age group (50-64, 65-70, 71-74 and 75+ years) and baseline values fitted as fixed effects and centre fitted as a random effect, where possible.

The analysis of the co-primary and secondary safety outcomes will be descriptive only. The number and percentage of participants in each group experiencing each safety outcome will be reported.

Days off work will be analysed using Poisson regression. Quality of life scores (EQ-5D) will be analysed using a mixed regression model, with treatment group, time point (day/visit at which the questionnaire was completed), age group and baseline EQ-5D score fitted as fixed effects and centre fitted as a random effect, where possible. An interaction between treatment group and time point (day/visit) will be included to enable the treatment effects of interest to be estimated.

Two subgroup analyses are planned. The first will be comparing anti-S Ig by COVID-19 vaccine in previous 6 months (yes/no); and the second will be comparing HAI by influenza vaccine in previous 6 months (yes/no). A third subgroup analysis will be considered if a significant number of participants in groups 2 and 3 have a COVID-19 infection between visit 1 and visit 3, comparing anti-S Ig between those who have had a COVID-19 infection between visits 1 and 3 and those who haven't.

Full details of the proposed models will be specified in the SAP. Model validity will be checked using standard methods; alternative models or transformations will be explored if model fit is inadequate. Findings will be reported as effect sizes and 95% confidence intervals.

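### Half of the second-dose RZV-alone safety controls come from the single-injection visit at day 112, so the pooled contrast mixes co-administration with visit and partial loss of masking

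*Protocol*

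**What the plan says.** Objective 9 in section 3 (Aims and objectives) defines the second-dose controls as "Grade 3 and 4 SSR after 2nd dose of RZV in group 1, 3 (day 112) and 4 (day 56"). The co-administered side of that objective is Group 2, which receives its second RZV dose together with C19 at day 56. Objective 11 names the same control groups and days, "compared to grade 3 and 4 SSR after 2nd dose RZV with aQIV in group 5", which Table 3 places at day 56. The Part A co-primary safety endpoint in section 4.1 is the rate of grade 3 and 4 solicited systemic reactions "after C19 vaccine/RZV (first or second dose, groups 2 and 3) and RZV alone 7 days after vaccination (groups 1-5"). Part B has the same form, with Groups 4 and 5 as the co-administered groups.

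Table 1 gives two injections at the first and second vaccination timepoints, with placebo as the second where needed. For visit 5 it says: "At the final vaccination visit participants will receive one injection". Table 3 shows RZV with no placebo at day 112 for Groups 1 and 3.

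The solicited events are recorded by participants in a 7-day diary (section 11), and the note to Table 2 assumes all of them to be related. Section 5.2 relies on participant blinding to limit performance and detection bias.

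On analysis, section 13.4 states: "The analysis of the co-primary and secondary safety outcomes will be descriptive only", with numbers and percentages reported by group. Section 4.2 also lists "Unsolicited Aes for 30 days after vaccination". An individual's participation ends at visit 6 (section 10), when Group 1 may also receive aQIV in season (Table 3, section 5.8.12).

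**The concern.** The exposure under study is receiving two vaccines together. All co-administered second doses are given at day 56 as two injections, so those participants cannot tell one active vaccine from two. Participants in Groups 1 and 3 at day 112 receive one injection and know that they are not being co-administered two vaccines. The outcome is self-reported fatigue, headache, myalgia and similar symptoms, graded mainly by limitation of activity. Because every event is assumed related, blinding the causality assessors gives no protection here. A single control rate over both visits therefore mixes co-administration with visit, number of injections and knowledge of exposure.

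This bears on a stated purpose of the trial. Section 2 names safety with the second RZV dose as a remaining evidence gap.

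Two related points follow from the same schedule. First-dose controls are spread over day 0 and day 56, whereas each co-administered group had its first dose at only one of those visits. Unsolicited events are compared over 30 days, but participation nominally ends 28 days after visit 5.

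**Working it through.** **Inputs.** Group sizes (Table 1): "120 participants to groups 1 and 2, and 240 participants to groups 3-5". Of Group 3, 120 continue to RZV (Table 1); section 5.8.2 says 129. Vaccines by visit come from Table 3 and visit windows from Table 4. The protocol gives no reaction rate and no sample size for safety, so the rates below are assumptions.

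**The plan's own total.** 120 + 120 + 3 × 240 = 960, as stated in section 13.1.

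**Where the RZV-alone doses fall.**

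| Dose | Group | Visit | Injections | n |
|---|---|---|---|---|
| 1 | 2 | day 0 | 2 | 120 |
| 1 | 5 | day 0 | 2 | 240 |
| 1 | 1 | day 56 | 2 | 120 |
| 2 | 4 | day 56 | 2 | 240 |
| 2 | 1 | day 112 | 1 | 120 |
| 2 | 3 (continuing) | day 112 | 1 | 120 |

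- Second dose, single-injection share: (120 + 120) / (120 + 120 + 240) = 240/480 = 50%. With 129 continuing in Group 3: 249/489 = 50.9%.
- If 5% to 10% drop out before day 112 only: 228/468 = 48.7% to 216/456 = 47.4%.
- Both doses: 240 / (480 + 480) = 240/960 = 25%.
- First dose, C19 contrast: Group 3 is at day 56, but 120 + 240 = 360 of 480 controls are at day 0. First dose, aQIV contrast: Group 4 is at day 0, and 120 of 480 controls are at day 56.

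**What a reporting difference would do (illustration only).** Suppose single-injection recipients report at f times the masked rate r. With half the controls affected, the pooled control rate is r(1 + f)/2, and with no true difference the apparent risk ratio is 2/(1 + f). For f = 0.7, 0.9 and 1.1 this gives 1.18, 1.05 and 0.95. Nothing in the protocol fixes f, or whether it lies below or above 1.

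**Precision of the restricted contrasts.** 95% half-width = 1.96 × √[p(1 − p)(1/n1 + 1/n2)], at an assumed p = 0.10:

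| Contrast | Pooled controls (480) | Restricted controls |
|---|---|---|
| Group 3, dose 1 (n = 120) | 6.0 points | v Group 1 (120): 7.6 |
| Group 4, dose 1 (n = 240) | 4.7 points | v Groups 2+5 (360): 4.9 |
| Group 2, dose 2 (n = 120) | 6.0 points | v Group 4 (240): 6.6 |
| Group 5, dose 2 (n = 240) | 4.7 points | v Group 4 (240): 5.4 |

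Groups 1 and 3 at day 112 also total 240, so contrasts with them have the same half-widths as those with Group 4. At p = 0.05 and 0.20, the Group 2 dose-2 half-width goes from 4.4 to 4.8 and from 8.0 to 8.8 points.

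**Unsolicited-event window after visit 5.** Visit 5 is day 112–116 and visit 6 is day 140–146. Nominal gap: 140 − 112 = 28 days. Shortest: 140 − 116 = 24. Longest: 146 − 112 = 34. Where visit 6 falls before day 30, in-season aQIV in Group 1 is given inside the 30-day window of its RZV-alone dose. After visit 3, participation continues well beyond 30 days.

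**The case against.** The strongest reply is that no conclusion depends on this. The safety endpoints are descriptive, and the success criteria in section 4.1 rest on immunogenicity alone. The objectives list control groups with their days and do not say outright that they are merged into one rate. Section 13.4 promises results by group, and section 4.2 promises solicited events by timepoint and group, so a reader could pick out Group 4 at day 56. This stands, and it limits the point to interpretation. It does not remove it: the contrast written into the objectives is still against the whole listed set, and nothing separates the two visits within that contrast.

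A second reply is that every group gets one injection at visit 5, which may be RZV, aQIV, C19 or placebo. A reader might infer that these controls are simply unblinded. They are not: they know one injection from two, but not the product. All first-dose controls had two injections, so for dose 1 only the visit difference applies.

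Third, Group 4 is not a clean replacement. It received aQIV with its first RZV dose and is itself a Part B co-administration group. Group 1 is the only second-dose control never given RZV with another vaccine. This stands, and it rules out making Group 4 the sole main comparator.

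Fourth, a reader might infer that day-112 controls are depleted of people who reacted earlier. The protocol does not show this: section 6.9 expects few withdrawals and section 12.6 expects loss below 5%.

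Last, a reader might infer that the diary closes at visit 6. Section 5.8.11 already asks for reporting to day 30 after visit 5. The difficulty is that section 10 ends participation at visit 6, so the two need reconciling.

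**Conclusion.** The point holds as one of interpretation. For second doses, 240 of 480 RZV-alone controls (47% to 51% under the variants shown) come from a single-injection visit, while every co-administered second dose is a two-injection dose at day 56. Over both doses the share is 25%. These shares follow from the planned group sizes and Table 3 and need no further assumption.

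The tempting stronger conclusion is that the design will produce a false excess of severe reactions with co-administration. The documents do not support it: the existence, size and direction of a reporting difference cannot be derived from them, and the risk ratios above are illustrations. No test, power figure or success criterion is affected. The change is worth making because the pooled contrast is hard to read as evidence on co-administration and the data for clearer contrasts are already being collected.

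**What to change.** - **Dose 1.** State the same-visit randomised contrasts beside the pooled ones: Group 4 v Groups 2+5 at day 0 (aQIV), and Group 3 v Group 1 at day 56 (C19).
- **Dose 2.** Beside the pooled rate, report the RZV-alone controls separately as Group 4 (day 56, two injections) and Groups 1 and 3 (day 112, one injection). Give a risk difference and 95% CI for Group 2 and for Group 5 against each. State that Group 4 had aQIV with dose 1, so neither control set is ideal.
- **Unsolicited events.** Reconcile the 30-day window with participation ending at visit 6, either by a common window for all doses or by following everyone to day 30 after visit 5. Separate events arising after Group 1's in-season aQIV at visit 6 from those after its RZV-alone dose.
- **Group 3.** Reconcile 120 (Table 1) with 129 (section 5.8.2) as the number continuing.

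The cost is a few table rows, at most 30 − 24 = 6 further days of event reporting if follow-up to day 30 is chosen, and wider intervals in the restricted contrasts. At an assumed 10% rate the largest increase is for Group 3 at dose 1, from 6.0 to 7.6 points; for Group 2 at dose 2 it is from 6.0 to 6.6.

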4.1 Primary outcome

Part A: Assessment of co-administration of COVID-19 and RZV

Co-Primary Endpoints

1) Immunogenicity of C19

Anti-S protein Ig concentrations expressed as Geometric Mean Concentrations (GMCs) for both strains in C19 vaccine/RZV (first or second dose, groups 2 & 3) and C19 vaccine alone (group 1), will be used to calculate between group ratios expressed a geometric mean ratio (GMR), at 1 month after vaccination with C19 vaccine.

2) Immunogenicity of RZV

Anti-gE Ig concentrations expressed as GMCs after co-administration of C19 vaccine/RZV (first or second dose) and RZV alone, 1 month after 2nd dose of RZV, and between-group ratios expressed as GMRs.

Success criteria:

Part A of the trial will be classified as a success if both of the following meet the success criteria:

- 1) The combined administration of C19 vaccine and RZV (first or second dose) will be considered non-inferior to C19 vaccine alone if the lower limit of the 95% confidence interval for the (GMR) of anti-S protein Ig concentrations exceeds 0.67, the standard WHO non-inferiority margin for recommendation of new vaccines.⁷, AND

2) The combined administration of C19 vaccine and RZV (first or second dose) will be considered non-inferior to RZV alone if the lower limit of the 95% confidence interval for the GMR of Anti-gE Ig concentrations exceeds 0.67.

3) Safety of RZV

The rate of grade 3 and 4 solicited systemic adverse reactions (Table 2) after C19 vaccine/RZV (first or second dose, groups 2 and 3) and RZV alone 7 days after vaccination (groups 1-5) This is a descriptive outcome.

Table 2 Solicited AEs collected on post vaccination diary cards

Systemic solicited AEs
Fatigue
Fever
GI symptoms†
Headache
Myalgia
Shivering

†Gastrointestinal symptoms include nausea, vomiting, diarrhoea and/or abdominal pain

Note: The above AEs are assumed to be related and will be classed as adverse reactions.

Part B: Assessment of co-administration of adjuvanted influenza vaccine and RZV

Co-Primary Endpoints

1) Immunogenicity of aQIV

HAI titres expressed as GMCs in aQIV/RZV (first or second dose, groups 4 & 5) and aQIV alone (group 3) will be used to calculate between group ratios, expressed as GMR at one month after aQIV vaccination.

2) Immunogenicity of RZV

Anti-gE Ig concentrations expressed as GMCs after co-administration of aQIV/RZV (first or second dose) and RZV alone, 1 month after 2nd dose of RZV, and between-group ratios expressed as GMRs.

Success criteria:

Part B of the trial will be classified as a success if both of the following meet the success criteria:

- 1) The combined administration of aQIV and RZV (first or second dose) will be considered non-inferior to aQIV (for 3 of the strains included in the vaccine; HAI influenza A H3N2, HAI influenza A H1N1 and HAI influenza B Victoria) alone if the lower limit of the 95% confidence interval for the GMR of HAI exceeds 0.67, the standard WHO non-inferiority margin for recommendation of new vaccines.⁷, AND
- 2) The combined administration of aQIV and RZV (first or second dose) will be considered non-inferior to RZV alone if the lower limit of the 95% confidence interval for the GMR of Anti-gE Ig concentrations exceeds 0.67.

3) Safety of RZV

The rate of grade 3 and 4 solicited systemic adverse reactions (Table 2) after aQIV/RZV (first or second dose, groups 4 and 5) and RZV alone 7 days after vaccination (groups 1-5). This is a descriptive outcome.

4.2 Secondary outcomes

Immunological

- Vaccine response rate (VRR) to RZV as measured by anti-gE, 1 month after vaccination with 2nd dose of RZV, in all groups and between-group differences. VRR defined as a 4-fold increase in post-vaccination anti-gE compared to pre-vaccination anti-gE

concentration for participants who are seronegative at baseline then a 4-fold increase compared to a cut-off value for seropositivity.

- Exploratory evaluation of cell-mediated immunology, CD4+T-cells responses 1 month after the 2nd dose of RZV as measured by intracellular cytokine staining (ICS) compared to RZV given alone or concomitantly for either first or second dose
- S and N-protein immunoglobulin, before and 1 month after vaccination with a single dose of RZV and aQIV to assess for exploratory immunology T-cells against SARS-CoV-2 provided by RZV vaccine or aQIV

Safety

- Percentage of participants reporting grade 3 and 4 SSR after first dose of RZV alone compared to first dose co-administered with either C19 vaccine or aQIV.
- Percentage of participants reporting grade 3 and 4 SSR after second dose of RZV alone compared to second dose co-administered with either C19 vaccine
- Percentage of participants reporting solicited local and systemic Aes, 7 days after each vaccination time point by group and between-group ratios
- Unsolicited Aes for 30 days after vaccination
- Serious adverse events throughout the study period
- Adverse events of special interest (pIMDs) throughout the study period
- Days off work (for participants in employment) during the study period reported as related to vaccination
- Quality of life score following vaccine co-administration compared to single vaccination in the 7 days after vaccination

Qualitative

Outcomes will include but not be limited to

- Participant acceptance of multiple vaccinations (2 or more) for future routine vaccinations
- Trial staff perceptions on offering multiple vaccinations (2 or more) for future routine vaccinations

5. Plan of Investigation

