1.1 Trial schema

Figure 1 Trial schema

Interested volunteers complete online expression of interest questionnaire					
↓					
Pre-screening of initially eligible volunteers by recruiting site					
↓					
Time point	Group				
	1	2	3	4	5
Visit 1 Day 0	All participants: Consent, medical history and physical examination, observations (including height, weight, temperature), eligibility confirmation, randomization and vaccination				
	Blood sample: S-protein and exploratory subset T-cells	Blood sample: gE serology, CD4+ and exploratory subset T-cells	Blood sample: HAI and exploratory subset T-cells	Blood sample: HAI and gE serology and CD4+ subset	Blood sample: gE serology and CD4+ subset
	C19 + Placebo	RZV + Placebo	aQIV + placebo	RZV + aQIV	RZV + placebo
Participant completes diary for 7 days and reports any hospitalisations or concerns.					
Half of the participants in group 3 will end the study here					
Visit 2 Day 26 - 32	All participants: safety review.				
	1	2	3	4	5
	Blood sample: S-protein and exploratory subset T-cells	Blood sample: exploratory subset T-cells	Blood sample: HAI and exploratory subset T-cells	Blood sample: HAI	-
Visit 3 Day 56-60	All participants: safety review, temperature and vaccination.				
	1	2	3	4	5
	Blood sample: gE serology and CD4+ subset	Blood sample: S-protein	Blood sample: S-protein, gE serology and CD4+ subset	-	Blood sample: HAI
	RZV + Placebo	RZV + C19	C19 + RZV	RZV + placebo	RZV + aQIV
Participant completes diary for 7 days and reports any hospitalisations or concerns.					
Visit 4 Day 82-86	All participants: safety review.				
	1	2	3	4	5
	-	Blood sample: S-protein, gE serology and CD4+subset	Blood sample: S-protein	Blood sample: gE serology and CD4+ subset	Blood sample: HAI, gE serology and CD4+ subset
Visit 5 Day 112-116	All participants: safety review, temperature and vaccination*.				
	1	2	3	4	5
	-	-	-	-	-
	RZV	aQIV or placebo*	RZV	C19 or placebo*	C19 or placebo*
Participant completes diary for 7 days and reports any hospitalisations or concerns.					
Visit 6 Day 140-146	All participants: safety review.				
	1	2	3	4	5
	Blood sample: gE serology and CD4+ subset	-	Blood sample: gE serology and CD4+ subset	-	-
	aQIV*				

*these vaccinations will be given if the visit is taking place during the winter vaccination season, if not, a placebo injection will be given instead for visit 5.

2. Background & Rationale

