9.3 Samples remaining after all testing for this trial is completed

Participants will be informed that there may be leftover samples of their blood (after all testing for this trial is completed). Participants will be able to decide if they permit future use of any leftover samples.

With the participants' informed consent, any leftover serum or peripheral blood mononuclear cells will be kept for future analysis of COVID-19 and other coronavirus-related diseases or vaccine-related responses and other future research (exploratory immunology), including genotypic testing of genetic polymorphisms potentially relevant to vaccine immunogenicity.

If a participant elects not to permit this, all that participants' leftover samples will be discarded at the end of the trial.

Samples that are to be stored for future research will be transferred to a licenced Research Tissue Bank.

10. Definition of end of trial

The definition of the end of the trial is the date when all participants have completed visit 6, or are lost to follow-up, all samples have been analysed, the database has been locked and all data queries have been resolved.

The end of the trial for an individual patient is defined as completion of visit 6 or loss to follow-up.

11. Safety data collection and reporting

Participants will be asked to complete an electronic diary of solicited local (pain, redness, and swelling at injection site) and systemic (fatigue, fever GI symptoms (nausea, vomiting, diarrhoea and/or abdominal pain) headache, myalgia, shivering) AEs for 7 days after each vaccination.

Participants will be asked to record unsolicited AEs, up to 30 days after vaccination. Participants would be counselled with regard to expected side effects during the consent process and in the diary training. Leaflets about side effects would also be provided for participants.

Serious adverse events and adverse events of special interest (pIMDs) should be collected until the study end.

Safety monitoring

Safety monitoring would be continuous throughout the whole study and performed in real-time for the first 7 days after vaccination in the following ways:

- Participants would be required to complete electronic diary cards that would be reviewed in real time by trial physicians and the trial coordination team. All events will be reviewed, and reports of any grade 3 or above will trigger an alert to the relevant teams.

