11.3 Period for recording adverse events

Data on serious adverse events, will be collected for the period the participant is taking part in the trial, i.e., from visit 1 to visit 6.

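### SAE and pIMD percentages by group cover unequal time after the second RZV dose (28 days in Groups 1 and 3, 84 in Groups 2, 4 and 5), and half of Group 3 is followed for only about 28 days in all

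*Protocol*

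**What the plan says.** Among the secondary safety outcomes, section 4.2 lists SAEs over the study and "Adverse events of special interest (pIMDs) throughout the study period". Key Secondary Objective 15 in section 3 covers SAEs and events of special interest, "including potential immune mediated disorders (pIMD) from after first vaccination until the study end".

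Collection follows the participant's time in the trial, not the date of an RZV dose. The opening of section 11 states: "Serious adverse events and adverse events of special interest (pIMDs) should be collected until the study end". Section 11.3 collects SAEs "for the period the participant is taking part in the trial, i.e., from visit 1 to visit 6". Section 10 adds: "The end of the trial for an individual patient is defined as completion of visit 6 or loss to follow-up". Figure 1 places that last visit at "Visit 6 Day 140-146".

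Section 13.4 makes the safety analysis descriptive: "The number and percentage of participants in each group experiencing each safety outcome will be reported".

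Table 3 (section 5.5) gives RZV at days 56 and 112 in Groups 1 and 3, and at days 0 and 56 in Groups 2, 4 and 5. The synopsis and Figure 1 say that half of Group 3 does not go on to the later vaccinations and receives no trial RZV.

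Other safety outcomes are tied to a dose: 7 days for solicited reactions and 30 days for unsolicited events. SAEs and pIMDs have no such window.

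**The concern.** The trial exists to judge whether RZV can be given with another vaccine, and the background section says safety data are still needed for co-administration at the second RZV dose. Readers will look across the group columns of the SAE and pIMD table for a sign of harm from co-administration. Those columns are alike in calendar time for completers, but not in time since RZV.

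Many conditions on the long pIMD list need not appear within a month. If RZV caused a late event, the schedule would let it be counted in Groups 2, 4 and 5 and would close observation before it could be counted in Group 1. An excess in the co-administration columns could then reflect when doses were scheduled.

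Group 3 has a separate problem. If its percentage uses everyone randomised, half of the denominator was observed for about a fifth of the time (28/140) and never received RZV.

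**Working it through.** **Inputs.** RZV days and co-administered vaccines: Table 3. Visit windows: Table 4 (visit 3, D56-60; visit 5, D112-116; visit 6, D140-146). End of collection: visit 6 (sections 10 and 11.3). Group sizes: 120, 120, 240, 240, 240, with 120 of Group 3 continuing (synopsis).

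**The plan's own figure.** The protocol gives about 5 months per participant. Day 140 is 140/28 = 5 four-week periods, or 140/30.44 = 4.6 calendar months. This agrees.

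**Nominal days observed = 140 minus day of dose.**

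| Group | RZV days | After dose 1 | After dose 2 | Planned person-days after dose 2 |
|---|---|---|---|---|
| 1 (both doses without another active vaccine) | 56, 112 | 84 | 28 | 120 × 28 = 3,360 |
| 2 (C19 with dose 2) | 0, 56 | 140 | 84 | 120 × 84 = 10,080 |
| 3, continuing (C19 with dose 1) | 56, 112 | 84 | 28 | 120 × 28 = 3,360 |
| 4 (aQIV with dose 1) | 0, 56 | 140 | 84 | 240 × 84 = 20,160 |
| 5 (aQIV with dose 2) | 0, 56 | 140 | 84 | 240 × 84 = 20,160 |

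The ratio is 84/28 = 3 after dose 2 and 140/84 = 1.67 after dose 1.

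**With visit windows, after dose 2.** Groups 1 and 3: from 140 − 116 = 24 to 146 − 112 = 34 days. Groups 2, 4 and 5: from 140 − 60 = 80 to 146 − 56 = 90 days.

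**What each group can show.** For a risk window of w days after dose 2, the share observed in Groups 1 and 3 is min(w, 28)/w. The protocol sets no window for these events, so the values of w are assumptions: 30 days gives 93%, 42 days 67%, 60 days 47% and 84 days 33%. In Groups 2, 4 and 5 the share is 100% for each.

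**Another exposure in the longer follow-up.** At visit 5, Groups 2, 4 and 5 may receive C19 or aQIV if in season, and placebo otherwise. Of their 84 days after dose 2, the first 112 − 56 = 56 precede that injection and the last 28 follow it.

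**Group 3 as randomised.** The non-continuing half attends visits 1 and 2 only (section 5.8.4; two visits' compensation in section 12.7). Mean follow-up is (120 × 140 + 120 × 28)/240 = 84 days, against 140 elsewhere. Section 5.8.2 gives 129 continuing participants, which would make it (129 × 140 + 111 × 28)/240 = 88 days.

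**The case against.** The strongest reply is that the planned table counts from first vaccination, not from dose 2, and that every completer has the same total time. That stands. A reader might turn the threefold difference in days into a threefold expected difference in SAE percentages with no true effect, but the documents do not support this. Suppose a constant background rate of 5, 10 or 20 SAEs per 100 person-years (assumed). Then 1 − exp(−rate × 140/365.25) gives 1.9%, 3.8% or 7.4% in every group of completers. The imbalance matters only for late events related to RZV. It matters for background events only in Group 3, if its non-continuing half is included.

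Second, a reader might infer that no late data exist after RZV given alone. Key Secondary Objectives 8 to 11 define RZV alone by dose, and for dose 2 they use Groups 1, 3 and 4. Group 4 receives its second dose with placebo and is followed for 84 days, so 240 of 120 + 120 + 240 = 480 planned second doses given alone have the longer observation. Group 4 had aQIV with dose 1, so it is not a clean control for the whole schedule, but the data exist. Continuing Group 3 participants also match Group 1 after both doses.

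Third, Objective 15 states no contrast of alone against co-administered, unsolicited events to 30 days after each RZV dose are already planned, and the synopsis asks for frequency and rate. An SAP may define a person-time denominator. These points limit the concern but do not remove it: the protocol fixes a whole-study window and a percentage per group, and no denominator can recover events after visit 6 in Groups 1 and 3.

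Finally, a 28-day table does not show late events. That is true. It makes the comparison fair within the window, and the limit beyond it has to be stated.

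**Conclusion.** The point holds as one of interpretation. The planned group percentages for SAEs and pIMDs are comparable in total time for completers, but not in time after RZV: 28 against 84 days after dose 2 (24 to 34 against 80 to 90 with visit windows). RZV-related events starting more than about a month after dose 2 cannot be seen in Group 1 and can be seen in Groups 2, 4 and 5. Group 3 is comparable in total time only if its two halves are separated.

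This assumes visits within their windows and collection that stops at visit 6. Section 5.8.12 allows clinically significant events to be followed up after participation, but no contact to find new ones is scheduled. No size can be put on any resulting bias, because the documents give no rate or onset time for late RZV-related events. The outcome is secondary and descriptive, so the success criteria of Parts A and B are untouched. The change is worth making because it is cheap and removes an ambiguity in the safety table.

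**What to change.** In sections 4.2 and 13.4:

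- Keep the whole-study listing of SAEs and pIMDs by group. Beside it, show person-days observed in total and after each RZV dose.
- Report the continuing and non-continuing parts of Group 3 separately.
- Add a table of SAEs and pIMDs by RZV dose, alone against co-administered, using the comparators already set in Key Secondary Objectives 8 to 11. Use a common window of about 28 days after each dose, among recipients of that dose. Give person-days as the denominator, since some participants are seen for as few as 24 days after dose 2.
- Base any statement on alone against co-administered on that table, and state that the trial cannot compare later-onset events after dose 2 with Group 1.

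The cost is one extra descriptive table from dates already collected, with no change to visits or vaccinations. The downside is that events after the window appear only in the whole-study listing.
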